## 8.2 Reporting Period

## 8.2.1 Adverse Event

AEs will be collected from the time of the first supervised brushing with the acclimatization dentifice and until 5 days following last administration of the investigational product.

Medical occurrences that begin before the start of study treatment but after obtaining informed consent will be recorded on the Medical History/Current Medical Conditions section of the case report form (CRF) not the AE section.

### 8.2.2 Serious Adverse Event

SAEs assessed as **not related** or **related** to study participation (e.g., investigational product, protocol mandated procedures, invasive tests, or change in existing therapy), or related/not related to a GSK concomitant medication will be recorded from the time a subject signs the ICF, which is obtained prior to the subject's participation in the study, i.e., prior to undergoing any study-related procedure and/or receiving investigational product and until 5 days following last administration of the investigational product.

## 8.3 Reporting Procedures

The investigator and any designees are responsible for detecting, documenting and reporting events that meet the definition of an AE or SAE and remain responsible for following up on AEs that are serious, considered related to the study treatment and/or the study, or that caused the participant to discontinue the study treatment.

The investigator is to report all directly observed AEs and all AEs spontaneously reported by the study subject. In addition, each study subject will be questioned about AEs.

Each AE is to be assessed to determine if it meets the criteria for SAEs. If an SAE occurs, expedited reporting will follow local and international regulations, as appropriate.

When an AE/SAE occurs, it is the responsibility of the investigator to review all documentation (eg, hospital progress notes, laboratory, and diagnostics reports) related to the event.

The investigator or site staff will then record all relevant information regarding an AE/SAE in the CRF.

It is **not** acceptable for the investigator to send photocopies of the participant's medical records to GSK in lieu of completion of the GSK AE/SAE CRF page.

There may be instances when copies of medical records for certain cases are requested by GSK. In this instance, all subject identifiers, with the exception of the subject number, will be blinded on the copies of the medical records prior to submission to GSK.

The investigator will attempt to establish a diagnosis of the event based on signs, symptoms, and/or other clinical information. In such cases, the diagnosis will be documented as the

GlaxoSmithKline Consumer Healthcare Confidential

Template Version Effective: 22-Jun-2017

Page 40 of 60

AE/SAE and not the individual signs/symptoms. Clinical AEs will be described by diagnosis and not by symptoms when possible (e.g., upper respiratory tract infection, seasonal allergy, etc. instead of runny nose).

Medical conditions reported prior to the time period for reporting AEs/SAEs should be recorded as part of the subject's medical history.

AEs elicited by the investigator in a standard manner at the study visits should also be recorded in the AE section of the CRF. Care will be taken not to introduce bias when detecting AE and/or SAE. Open-ended and non-leading verbal questioning of the participant is the preferred method to inquire about AE occurrence.

### 8.3.1 Adverse Event

All AEs will be reported on the AE page(s) of the CRF by the investigator or site staff. It should be noted that the form for collection of SAE information is not the same as the AE CRF. Where the same data are collected, the forms must be completed in a consistent manner. For example, the same AE term should be used on both forms. AE should be reported using concise medical terminology on the CRF as well as on the form for collection of SAE information.

### 8.3.2 Serious Adverse Event

A paper copy of the SAE form provided in the investigator study master file should be completed as fully as possible.

It is essential to enter the following information:

- Protocol and subject identifiers
- Subject's demography
- Description of events, with diagnosis if available
- Investigator opinion of relationship to study product
- Criterion for seriousness.

The following are desirable and are of particular relevance for investigator and GSK CH assessment of the SAE report:

- Date of onset of AE
- Date AE stopped, if relevant
- Study product start date
- Study product end date if relevant
- Action taken on study product
- Outcome if known

The SAE form, completed as fully as possible, must be e-mailed to the GSK CH Clinical Operations Safety Reporting email box with the study number and subject number in the

GlaxoSmithKline Consumer Healthcare Confidential Template Version Effective: 22-Jun-2017 Page **41** of **60** 

	Document Name	208153 Clinical Protocol.docx		
	Туре	Version	Document Identifier	Effective Date
	eldo clinical doc	3.0; Most-Recent; Effective; CURRENT	090032d580d852b1	3-Aug-2017 05:58:20
	Reason For Issue	Auto Issue		•
t	annous fluoride			

Final 1.0 Clinical Protocol

subject line of the email **immediately and under no circumstance should this exceed 24 hours** after study site personnel learn of the event. The investigator will submit any updated SAE data to the sponsor, **immediately and under no circumstance should this exceed** 24 hours of it being available. The GSK CH Study Manager should also be notified of the situation by telephone or email.

#### **Email Serious Adverse Events to:**

PPD

The GSK CH Study Manager or designee will be responsible for forwarding the SAE form to the Case Management Group, Global Clinical Safety and Pharmacovigilance mailbox

The initial report will be followed up with more information as relevant, or as requested by the GSK CH study manager.

#### 8.3.3 Sponsor's Reporting Requirements to Regulatory Authorities and Ethics Committees

GSK has a legal responsibility to notify, as appropriate, the local regulatory authority and other regulatory authorities about the safety of a product under clinical investigation. Prompt notification of SAEs by the investigator to GSK is essential so that legal obligations and ethical responsibilities towards the safety of subjects are met.

GSK will comply with country specific regulatory requirements relating to safety reporting to the regulatory authority, IEC and investigators.

Investigator safety reports must be prepared for suspected unexpected serious adverse reactions (SUSAR) according to local regulatory requirements and sponsor policy and forwarded to investigators as necessary.

An investigator who receives an investigator safety report describing a SAE or other specific safety information eg, summary or listing of SAE) from the sponsor will review and then file it along with the Safety Statement and will notify the IEC, if appropriate according to local requirements.

## 8.4 Evaluating Adverse Events and Serious Adverse Events

#### 8.4.1 Severity Assessment

The investigator or designee will make an assessment of severity for each AE and SAE reported during the study and will assign it to one of the following categories:

• Mild: An event that is easily tolerated by the subject, causing minimal discomfort and not interfering with everyday activities.

GlaxoSmithKline Consumer Healthcare Confidential Template Version Effective: 22-Jun-2017 Page **42** of **60** 

- Moderate: An event that is sufficiently discomforting to interfere with normal
  - everyday activities
  - Severe: An event that prevents normal everyday activities.

Note: An AE that is assessed as severe will not be confused with an SAE. Severity is a category utilized for rating the intensity of an event; and both AEs and SAEs can be assessed as severe. For example, a headache may be severe (interferes significantly with the subject's usual function) but would not be classified as serious unless it met one of the criteria for SAEs, listed above.

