#### 10.2.5 Safety Analyses

Safety population will be used for safety assessments. Safety analyses will be performed according to the treatment that the subject received (using variable ATRT). All AEs will be reviewed by the Clinical Research Scientist or Designee prior to database lock and unblinding and will be coded using the Medical Dictionary for Regulatory Activities (MedDRA). During this review stage, AEs will be further categorized as oral or non-oral. AEs will be listed and summarized by treatment received. Serious AEs will also be listed. AEs will be regarded as treatment emergent if they occur on or after the first treatment application at the baseline visit. The following AEs tables split by treatment will be produced:

- Listing of all AEs (including Non-treatment emergent AEs from all subjects)
- Listing of all AEs for screened subjects
- Treatment emergent AEs by Oral/Non-Oral Preferred Term (PT)
- Treatment emergent AEs by System Organ Class (SOC) and PT
- Treatment emergent AEs by SOC, PT and intensity
- Treatment emergent treatment related AEs by Oral/Non-Oral
- Treatment emergent treatment related AEs by SOC and PT
- Listing of SAEs (if there are none a null listing will be produced; if there are more than 5 treatment emergent serious SAEs a table will be produced instead by SOC and PT)
- Non-serious treatment emergent AEs by SOC and PT (only produced if there are more than 5 SAEs)

OST abnormalities will be listed and tabulated. The tabulation will show changes in abnormality from baseline to each follow-up assessment.

Exposure to study product will also be tabulated and listed by treatment group.

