
10.2.1 Demographic and Baseline Characteristics
 
Descriptive statistics (percentages, means and standard deviations) of demographic baseline characteristics, medical history, current/concomitant medication and compliance will be tabulated.
	
4.2.2 General Medical History
 
Medical history data will be listed (Listing 16.2.4.2) with start date and end date or ongoing at the start of study drug.
 
5.1.1 Prior and Concomitant Medication
 
Concomitant medications will be listed by subject, with, indication, dose, dose form, frequency, route, start date and end date
	For medical history and concomitant medication coding is not done so listing will be produced.

10.2.5 Safety Analyses
 
Treatment emergent AEs by SOC, PT and intensity
 
OST abnormalities will be listed and tabulated. The tabulation will show changes in abnormality from baseline to each follow-up assessment.
 
Exposure to study product will
	
4.7.1 Adverse Events and Serious Adverse Events
 
OST abnormalities will be listed
 
4.3.1 Study Product Compliance and Exposure
 
Exposure to the study product will be listed in the listing
	
1) TEAEs by SOC, PT and intensity is study specific and it is decided to not produce for this study
 
2) In the same listing we can display

Protocol	Reporting & Analysis Plan	
Statistical Analysis section	Statistical Analysis Plan	Rationale for Changes
also be tabulated and listed by treatment group.		the changes in OST 3) To keep consistency across oral studies.

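### The SAP withdraws the protocol's only by-arm table of AE severity without a substantive reason, so no listed AE table summarises severity by arm

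*Protocol*

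**What the plan says.** Protocol 8.4.1 requires grading throughout: "The investigator or designee will make an assessment of severity for each AE and SAE reported during the study". It gives one three-level scale. Mild does not interfere with everyday activities. Moderate is "An event that is sufficiently discomforting to interfere with normal" everyday activities. The top level reads "Severe: An event that prevents normal everyday activities". A Note below the scale opens with "An AE that is assessed as severe will not be confused with an SAE" and illustrates the distinction: "For example, a headache may be severe (interferes significantly with the" subject's usual function).

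Protocol 10.2.5 includes "Treatment emergent AEs by SOC, PT and intensity" among the AE outputs to be split by treatment.

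SAP Section 5, which sets out changes from the protocol, quotes that item and withdraws it: "TEAEs by SOC, PT and intensity is study specific and it is decided to not produce for this study". The same row also replaces two other tabulations, of oral soft tissue (OST) changes and of exposure, with listings. SAP 4.7.1 then names the AE tables and listings to be presented by treatment group. The template for Listing 16.2.7.1 (all AEs, headed by treatment group) has a combined column for frequency and intensity.

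**The concern.** The protocol's safety objective covers oral tolerability as well as safety, and the SAP's only safety endpoint is adverse events. For a toothpaste, how bad the oral reactions are matters to tolerability alongside how many subjects have one. The investigator's team is asked to grade every event, and the protocol promised to summarise the grades by arm. After the SAP change the grades are still collected, but no listed table reports them.

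At stake is the report's ability to state, by arm and with denominators, how many subjects had moderate or severe events. Without the table, two products with similar AE counts and different severity profiles would have similar AE tables. A reader would have to find the difference by working through a subject-level listing.

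**Working it through.** There is no stated figure to reproduce. The check sets the planned outputs side by side.

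**1. Tables in the protocol and in the SAP**

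| Protocol 10.2.5 | SAP 4.7.1 | Split by severity? |
|---|---|---|
| Oral/non-oral and PT | Table 14.3.1.2 | No |
| SOC and PT | Table 14.3.1.1 | No |
| SOC, PT and intensity | None | Yes (protocol only) |
| Treatment-related, oral/non-oral | Table 14.3.1.4 | No |
| Treatment-related, SOC and PT | Table 14.3.1.3 | No |
| SAEs, tabulated only above a count of 5 | Table 14.3.1.5, same threshold | No |
| Non-serious events, only if more than 5 SAEs | Table 14.3.1.6, same threshold | No |

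The protocol has 5 unconditional and 2 conditional tables, 7 in all, and 1 is by severity. The SAP has 4 unconditional and 2 conditional tables, 6 in all, and 0 are by severity. The only table lost is the only one that carried severity.

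**2. The reason given.** Calling the table study-specific means that each study decides whether to have it. This study had decided, in its protocol. Other rows and items in the same SAP section do give reasons: medical history and concomitant medication are listed because they are not coded, and OST changes are said to be visible in the listing. The intensity item has no comparable reason.

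**3. What remains of severity.** Among the templates shown, intensity appears in the layout of Listing 16.2.7.1, which Listing 16.2.7.2 repeats for non-randomized subjects. A listing gives no counts, denominators or percentages by arm. Footnote [3] to the column expands two frequency abbreviations and says nothing about intensity. The body of the listing is blacked out, so it is not known whether intensity is coded or printed in words.

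**4. Illustration of what count-only tables cannot show.** The documents give no AE rates, so the counts here are assumptions. With about 180 subjects randomized and equal allocation assumed, each arm has 180/3 = 60. Suppose 10 subjects in each arm have an oral AE, of which 1 on the negative control and 7 on the Test Product are moderate or severe.
- Planned tables: 10/60 = 16.7% against 10/60 = 16.7%.
- Severity table: 1/60 = 1.7% against 7/60 = 11.7%, a difference of 10.0 percentage points.
- Range: with 10 affected subjects per arm, the number moderate or worse can be 0 to 10 in each arm. The unseen difference can therefore lie anywhere from 0 to 10/60 = 16.7 points, in either direction.

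This shows what the tables could conceal. It does not predict a result.

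**5. The scale and the Note.** On the scale, interference is Moderate and prevention is Severe. The Note's example attaches the word severe to significant interference. An event that interferes significantly without preventing activity is therefore Moderate on the scale and severe in the example. The mismatch is confined to the Moderate/Severe boundary. It is separate from the dropped table, and the illustration in step 4 does not bear on it, because that example pools moderate with severe.

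**The case against.** The strongest defence is that the change is declared. SAP Section 5 quotes the protocol item and says openly that it will not be produced. Intensity is still listed by treatment group, and SAP 4.7.1 also plans listings of oral treatment-emergent AEs, AEs leading to withdrawal, non-fatal SAEs and deaths. Their column layouts are not shown, and the full list of displays is in an attached worksheet that is not reproduced, so some may also carry intensity. A product with worse oral reactions would thus not be invisible. No hypothesis about severity is tested. All of this stands. It limits the point to one descriptive summary, but it supplies neither a reason for dropping that summary nor a replacement for it.

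A reader might go further and infer that the protocol has two definitions of severe, so that severity cannot be compared reliably between arms. The documents do not support that:
- The Note says significant interference, not interference alone. It is a parenthesis in an example whose stated purpose is to separate severe from serious.
- Raters are told to assign one of the three categories. That one scale applies to every arm at a single centre, so ambiguity at the upper boundary would mainly blur Moderate against Severe in all arms alike.
- Test and control tubes are overwrapped and dispensed in blinded fashion (protocol 5.4.1 and 5.4.2). The study is only examiner-blind and blinding of the AE rater is not separately stated, so differential grading is possible, but nothing in the documents shows it.

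**Conclusion.** The point holds for the dropped table. The SAP removes the one by-arm severity summary that the protocol planned, its stated reason is not substantive, and no table listed in SAP 4.7.1 replaces it. The size is one descriptive output: no test, p-value or efficacy conclusion changes. Restoring it is worthwhile because the grades are collected anyway and tolerability is a stated objective.

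The Note's example and the listing footnote are clerical matters and would not justify a comment alone. The conclusion rests on the tables named in SAP 4.7.1; if the unreproduced worksheet already contains a severity table, SAP Sections 4.7.1 and 5 would need correcting to say so.

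**What to change.** 1. In SAP 4.7.1, reinstate the by-treatment table of treatment-emergent AEs by SOC, PT and intensity from protocol 10.2.5. The shell should state how a subject with several events of different intensity is counted. An intensity split of the oral/non-oral table would be useful, but the protocol did not ask for it, so it is optional.
2. In SAP Section 5, remove only the intensity item and rationale item 1 from the row on safety analyses. Keep the rest of the row: it declares the changes to the OST and exposure tabulations, and deleting it would leave those undeclared. If the sponsor prefers not to restore the table, replace rationale item 1 with a real reason.
3. As minor tidying, reconcile the Note's example in protocol 8.4.1 with the Severe category, or have the Note refer to the scale. Define any intensity codes used in Listing 16.2.7.1.

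The cost is one table from data already collected, an edit to one row of SAP Section 5, one sentence in the protocol and possibly one footnote. If this is done before unblinding, the summary remains prespecified.

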## 8.4.2 Causality Assessment

The causality assessment is one of the criteria used when determining regulatory reporting requirements. For each AE/SAE, the investigator **must** document in the medical notes that he/she has reviewed the AE/SAE and has provided an assessment of causality. The investigator's assessment of causality must be provided for all AEs (serious and non-serious); the investigator must record the causal relationship in the CRF, as appropriate, and report such an assessment in accordance with the SAE reporting requirements if applicable.

A "reasonable possibility" of a relationship conveys that there are facts, evidence, and/or arguments to suggest a causal relationship, rather than a relationship cannot be ruled out. Generally, the facts (evidence) or arguments to suggest a causal relationship should be provided.

The investigator will use clinical judgment to determine the relationship and will also consult the Safety Statement and/or Product Information, for marketed products, in the determination of his/her assessment. Alternative causes, such as underlying disease(s), concomitant therapy, other risk factors, and the temporal relationship of the event to the study product will be considered and investigated.

There may be situations when an SAE has occurred and the investigator has minimal information to include in the initial report to GSK. However, it is very important that the investigator always make an assessment of causality for every event prior to the initial transmission of the SAE data to GSK. The investigator may change his/her opinion of causality in light of follow-up information and send an SAE follow-up report with the updated causality assessment.

## 8.5 Withdrawal Due to an Adverse Event and Serious Adverse Events

Withdrawal due to AEs should be distinguished from withdrawal due to other causes, according to the definition of AE noted earlier, and recorded on the appropriate AE CRF page.

When a subject withdraws because of an SAE, the SAE must be reported in accordance with the reporting requirements defined below.

GlaxoSmithKline Consumer Healthcare Confidential Template Version Effective: 22-Jun-2017 Page **43** of **60** 

Final 1.0 Clinical Protocol

## 8.6 Pregnancy

## 8.6.1 Time Period for Collecting Pregnancy Information

Pregnancy information will be collected on all pregnancies reported following administration of any investigational product or acclimatization product and until 5 days after the last dose.

#### 8.6.2 Action to be Taken if Pregnancy Occurs

The investigator will collect pregnancy information on any subject who becomes pregnant while participating in the study after administration of the investigational product or washout product. The investigator will record pregnancy information on the appropriate form and e-mail it to the GSK CH Clinical Operations Safety Reporting email box PPD

within 24 hours of learning of the subject becoming pregnant. The GSK CH Study Manager or designee will be responsible for forwarding the pregnancy information form to the Case Management Group, Global Clinical Safety and Pharmacovigilance mailbox PPD

The subject will be followed to determine the outcome of the pregnancy. Information on the status of the mother and infant / neonate (including concomitant medications taken by the mother during the pregnancy) will be forwarded by the investigator to the GSK CH Clinical Operations Safety Reporting email box and the GSK CH Study Manager or designee will forward this information to the Case Management Group, Global Clinical Safety and Pharmacovigilance group mailbox at GSK PPD Generally, follow-up will be no longer than 6 to 8 weeks following the estimated delivery date. Any termination of the pregnancy will be reported.

While pregnancy itself is not considered to be an AE, abnormal pregnancy outcomes (eg, spontaneous abortion, fetal death, stillbirth, congenital anomalies, ectopic pregnancy) are considered to be and should be recorded as an SAE.

Any female participant who becomes pregnant while participating will discontinue study treatment.

